### Appendix 3. Derivative variables for apatinib/placebo

Variable	Apatinib/Placebo
Protocol-Specified Method of Administration	Once a day, 750 mg each time, every 4 weeks in a treatment cycle
Duration of Drug Exposure (days)	Date of last administration - date of first administration + 1
Planned Duration of Treatment (days)	Date of last administration - date of first administration + 1
Actual Cumulative Doses of All Cycles (mg)	Summarize the actual dose (mg) in all treatment cycles: [duration of drug exposure (day) - (end date of dose modification - start date of dose modification) (day)] × 750 (mg) + (end date of dose modification - start date of dose modification) (day) × dose after modification (mg) - (end date of dose interruption - start date of drug interruption) (day) × interrupted dose (mg)
Planned Dose Intensity (mg/day)	750 (mg/day)
Actual Dose Intensity (mg/day)	Actual cumulative dose in all treatment cycles (mg) / [planned duration of treatment (day)]
Relative Dose Intensity (%)	100 × [actual dose intensity (mg/day)] / [planned dose intensity (mg/day)]

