4.5.2 Dose

Treatment group: Apatinib, 750 mg, q.d.; The dose can be reduced according to toxicity, with the first reduction to 500 mg, q.d., and the second reduction to 250 mg, q.d.; each treatment cycle contains 28 days.

Placebo group: Placebo, q.d. Each treatment cycle contains 28 days.

Considerations for the use of 750 mg in the treatment group:

1. According to the phase I PK data, the C_{max} and AUC of the 850 mg group were both higher than those of the 750 mg group, and it was speculated that the toxicity of the 850 mg group might be higher than that of the 750 mg group;
2. According to the phase II study of apatinib in HCC, the efficacy of the 850 mg group was comparable to that of the 750 mg group (TTP, OS; the DCR in the 850 mg group was slightly higher than that in the 750 mg group); 9 patients in the 850 mg group withdrew from the study due to adverse events with the duration of treatment less than 1 cycle (including 4 cases of gastrointestinal hemorrhage), while 3 patients in the 750 mg group withdrew from the study due to adverse events with the duration of treatment less than 1 cycle (no hemorrhage). Considering that the primary endpoint of phase III trial is OS, the dose of 750 mg, which showed better tolerability in HCC patients, is selected for the study.

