7.2.2 Dose interruption

The total duration of drug interruption during each treatment cycle should not be more than 2 weeks, so as to maintain the intensity of the study treatment received by the subjects.

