#### **7.4.2 Drug exposure and dose modification**

The drug exposure in the two groups is described using mean, standard deviation, maximum, minimum, and median.

The treatment interruption and dose modification during the trial are summarized.

The duration of drug exposure, actual dose intensity, and relative dose intensity of apatinib and placebo are summarized using mean, standard deviation, median, maximum, and minimum.

The specific definition rules of derived variables for the study drugs apatinib and placebo are shown in Appendix 3.

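### SAP Appendix 3 counts exposure days with + 1 but interruption and modification days as end minus start, and never defines the end date, so dose intensity can come out too high

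*SAP*

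**What the plan says.** SAP Appendix 3 defines the exposure variables.

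- Duration of exposure is "Date of last administration - date of first administration + 1". The planned duration of treatment has the same definition.
- The planned regimen is "Once a day, 750 mg each time, every 4 weeks in a treatment cycle", so planned dose intensity is 750 mg/day.
- Actual cumulative dose starts from exposure days at 750 mg. Days on a modified dose, measured as ("end date of dose modification - start date of dose modification) (day"), are re-priced at the modified dose. Interrupted days, measured as ("end date of dose interruption - start date of drug interruption) (day"), are then subtracted at the interrupted dose.
- Actual dose intensity is "Actual cumulative dose in all treatment cycles (mg) / [planned duration of treatment (day"; relative dose intensity (RDI) divides that by 750 mg/day.

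SAP 7.4.2 gives the use: "The duration of drug exposure, actual dose intensity, and relative dose intensity of apatinib and placebo are summarized using mean" and other descriptive statistics. Protocol 7.2 asks for dose intensity and interruption time in the final report.

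**The concern.** Exposure days, modified days and interrupted days are added and subtracted in one expression, so they need one day-counting convention. The first carries + 1 and the other two do not. End minus start is a correct length only when the end date is the first day of the next state. It is one day short when the end date is the last day of the episode. The SAP does not say which is meant.

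The SAP's other durations point to the inclusive reading. Efficacy times, OS and PFS in SAP 7.1.3 and time to first event of special interest in SAP 7.4.1 all add 1. On that reading each interruption or reduction is under-counted by a day and too much drug is credited.

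At stake is the accuracy and reproducibility of the exposure tables. Protocol 7.2.1 ties interruptions and reductions to toxicity, so more episodes, and more error, would be expected on the active arm. That is an expectation; the documents give no episode counts for this trial.

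**Working it through.** The documents give no numerical dose-intensity result, so there is no figure to reproduce. The check applies the Appendix 3 formula literally and compares it with a day-by-day sum of doses.

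**Inputs.** Full dose is 750 mg/day (SAP Appendix 3). The reduced levels come from Protocol 4.5.2: "with the first reduction to 500 mg, q.d., and the second reduction to 250 mg, q.d". The course lengths and episodes below are illustrative assumptions. L is the number of exposure days. With no episode and L = 28, the formula gives 28 × 750 = 21,000 mg and RDI 100%, as it should.

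**Reading (a): end date is the last affected day.** Each episode is one day short, whatever its length.

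- Interruption at dose d: excess d mg, or 100 × d / (750 × L) RDI points. At 750 mg this is 100/L.
- Reduction to dose d: excess (750 − d) mg, or 100 × (750 − d) / (750 × L) points. For 500 mg this is 33.3/L.

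One 7-day gap at 750 mg on days 15 to 21 is counted as 21 − 15 = 6 days:

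| L | Formula (mg) | Formula RDI | Daily sum (mg) | True RDI |
|---|---|---|---|---|
| 28 | 22 × 750 = 16,500 | 78.57% | 21 × 750 = 15,750 | 75.00% |
| 56 | 50 × 750 = 37,500 | 89.29% | 49 × 750 = 36,750 | 87.50% |
| 84 | 78 × 750 = 58,500 | 92.86% | 77 × 750 = 57,750 | 91.67% |
| 112 | 106 × 750 = 79,500 | 94.64% | 105 × 750 = 78,750 | 93.75% |

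A 1-day gap has start equal to end and counts as zero. Over 28 days RDI is 100.0% against 27/28 = 96.43%.

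Errors add across episodes. Protocol 7.2.2 says "The total duration of drug interruption during each treatment cycle should not be more than 2 weeks", which caps total time off but not the number of gaps. Four 3-day gaps in 84 days are counted as 4 × 2 = 8 days instead of 12: 76/84 = 90.5% against 72/84 = 85.7%.

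**Reading (b): end date is the restart or change day.** The same 7-day gap runs from day 15 to day 22, and 22 − 15 = 7. Over 28 days the formula gives 75.00%, which is exact.

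A reduction that lasts to the final dose has no change day. Take 84 days with 500 mg on days 29 to 84, closed on the last administration date:

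- Formula: 84 − 29 = 55 days, so (84 − 55) × 750 + 55 × 500 = 21,750 + 27,500 = 49,250 mg; 49,250/63,000 = 78.2%.
- Daily sum: 28 × 750 + 56 × 500 = 49,000 mg; 49,000/63,000 = 77.8%.

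**A combined course.** Over 84 days: off drug on days 15 to 21 (from 750 mg), 500 mg from day 22 to the end, off again on days 43 to 49 (from 500 mg).

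- Daily sum: 14 × 750 + 56 × 500 = 38,500 mg, 61.11%.
- Reading (a): 22 × 750 + 62 × 500 − 6 × 750 − 6 × 500 = 40,000 mg, 63.49%.
- Reading (b), reduction closed on day 84: 22 × 750 + 62 × 500 − 7 × 750 − 7 × 500 = 38,750 mg, 61.51%.

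**Adding + 1 without a definition.** If the recorded end is the restart day, the 7-day gap in 28 days becomes 8 days: 20 × 750 = 15,000 mg, or 71.43% against a true 75.00%.

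**The case against.** The strongest reply is that mixed notation is not in itself an error. Every interruption inside the exposure window has a restart date, because exposure ends at the last administration. If the forms record that date, end minus start is right. What they record would be settled by the Drug Interruption and Dose Modification forms listed in the Schedule of Activities and by the eCRF completion guide (Protocol 12.1.1), whose contents are not in the documents. This stands: a reader might infer that every episode certainly loses a day, and the documents do not establish that.

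Nor is a reduction lasting to the final dose miscounted under every coding. If it is closed on the day after the last dose, 56 days are counted and 77.8% is exact. The SAP states no such convention, so the case remains open.

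The direction is not guaranteed either. If a final interruption that never restarts were entered as an interruption (an assumption), the formula would subtract days outside the exposure window and understate dose.

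A reader might also infer that apatinib will look better tolerated than it was. The documents do not support that. SAP 7.4.1 separately summarises adverse events leading to interruption, reduction and discontinuation, SAP 7.4.2 separately summarises interruptions and modifications, and no test or decision rule uses dose intensity.

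The reply does not remove the undefined term, or the SAP's inclusive habit elsewhere, which makes reading (a) the more natural one.

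**Conclusion.** The point holds conditionally. Appendix 3 mixes two day conventions and leaves the end date undefined.

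- **On the more natural reading,** the error per 750 mg interruption is 100/L points, from 3.6 at 28 days to 0.9 at 112. A reduction to 500 mg costs 33.3/L, from 1.2 to 0.3 over the same range.
- **On the other reading,** resolved episodes are exact. The residual error is confined to a reduction still in force at the last dose and closed on that date, 0.4 points in the 84-day example. Such courses are foreseeable, because Protocol 7.1 and 7.2.3 bar re-escalation after a repeat reduction.

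The sizes rest on illustrative courses, not trial data. The consequence is limited to descriptive exposure summaries; OS and the other efficacy analyses are untouched. This is a minor correction worth making before the exposure tables are programmed.

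**What to change.** Preferred: compute actual cumulative dose as the sum of daily doses actually taken from first to last administration. This needs no interval convention, handles a reduction running to the end, and ignores days after the last dose.

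Alternative: define the end date as the last affected day for both interruptions and modifications, and use end − start + 1 for both. State that an episode in force at the last dose ends on the last administration date. First check what the eCRF forms record. Restart dates must be converted, or the extra day over-subtracts. Where one dose period's end date equals the next one's start date (Protocol Table 8 allows successive changes), the changeover day must be counted once.

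The cost is a small change to the derivation plus that check of the collected dates. Reported dose intensity may become slightly lower.

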7.2.5 Discontinuation criteria based on prolonged QT interval

1) If the patient's ECG shows QTcF > 480 ms, the use of apatinib should be interrupted, and the following measures should be immediately taken:

- (1) Immediately notify the sponsor, safety monitoring committee or scientific committee;
- (2) Analyze serum potassium and magnesium, and if it is lower than the lower limit of normal, use supplements to correct serum potassium and magnesium to within the normal range;
- (3) The concomitant medication must be reviewed;
- (4) The use of apatinib and the compliance with the dose must be verified;
- (5) Perform an ECG examination within 1 h after the first episode of QTcF > 480 ms;
- (6) If QTcF is still > 480 ms, repeat the ECG examinations at least once a day when clinically needed, until QTcF is < 480 ms;
- (7) If QTcF is still > 480 ms in repeated measurements and lasts for more than 2 weeks, apatinib treatment must be discontinued.

2) Guidelines for resuming drug administration:

- (1) If the cause of QTcF prolongation (except apatinib) is determined, and if QTcF returns to < 450 ms within 2 weeks after correction and is within 20 ms of the baseline value, apatinib treatment can be resumed at the same dose;

(2) If the cause of QTcF prolongation cannot be determined, and if QTcF returns to < 450 ms within 2 weeks and is within 20 ms of the baseline value, apatinib treatment can be resumed at the same dose;

(3) If QTcF exceeds 480 ms again after the subject is exposed to the investigational drug again, the use of the investigational drug should be discontinued;

(4) After the subject is exposed to the investigational drug again, if QTcF is prolonged by more than 20 ms from baseline or is between 450 and 480 ms and lasts for more than 2 weeks, the dose of the investigational drug should be modified as follows:

- Reduced from apatinib, 750 mg, q.d. to apatinib, 500 mg, q.d.;
- Reduced from apatinib, 500 mg, q.d. to apatinib, 250 mg, q.d.;
- Withdrawal.

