7.2.6 Discontinuation criteria based on liver function

1) If the subject has $ALT > 5 \times ULN$ and total bilirubin $> 2 \times ULN$, the following measures must be taken:

(1) Immediately discontinue the use of the investigational drug and give active symptomatic treatments;

(2) Complete the SAE form and handle it in accordance with the requirements for SAE in Section 11 of this protocol;

(3) Follow-up the event according to the requirements for "Follow-up of Adverse Events" in Section 4 of this protocol, and check liver function every week until it returns to the baseline level;

7.3 If the subject experiences any of the following conditions:

$ALT > 8 \times ULN$ or $ALT > 5 \times ULN$ for more than 2 weeks: The patient must be reexamined within 3 days after the first occurrence of the event, and then reexamined weekly to monitor whether the ALT value continues to increase. If the ALT value continues to increase, the use of the apatinib should be interrupted. The liver function should be reexamined within 2 weeks. If the treatment is effective and the subject is willing to continue to receive the apatinib treatment after obtaining the results of the liver function test, the subject can resume the apatinib treatment at the next lower dose level after obtaining the permission of the investigator and the medical director of the sponsor, and the liver function of the patient should be monitored every 2 weeks until it returns to the baseline level.

Other rules

To ensure the consistency of dose modifications throughout the study, treatment should be first discontinued before undergoing a dose modification for each dose cycle. The dose can only be reduced if the subject still cannot tolerate the dose after dose interruption.

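### SAP Appendix 3 does not confine subtracted interruption days to the dosing period, so dose intensity can be too low or uncomputable for patients who interrupt and never resume

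*SAP*

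**What the plan says.** SAP section 7.4.2 plans summaries of exposure duration, actual dose intensity and relative dose intensity for both groups and refers to Appendix 3 for the definitions. Protocol section 7.2 also requires dose intensity and interruption time in the final study report.

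Appendix 3 defines the quantities as follows:

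- Duration of drug exposure and planned duration of treatment have the same definition: "Date of last administration - date of first administration + 1".
- Actual cumulative dose starts from exposure days at 750 mg and replaces modified-dose days by the modified dose. It then subtracts ("end date of dose interruption - start date of drug interruption) (day) × interrupted dose (mg").
- Actual dose intensity is cumulative dose divided by planned duration. Planned dose intensity is 750 mg/day, and relative dose intensity is the ratio of the two as a percentage.

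The protocol describes an interruption that turns into a permanent stop. Section 7.2.5 interrupts drug when QTcF exceeds 480 ms and continues: "If QTcF is still > 480 ms in repeated measurements and lasts for more than 2 weeks, apatinib treatment must be discontinued".

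**The concern.** The exposure term and the subtracted term cover different periods. Exposure stops at the last dose taken. The interruption term runs for the recorded length of the interruption, wherever it lies. For a pause that the patient comes back from, the missed days lie between first and last dose and the subtraction is right. For a pause that the patient never comes back from, the missed days lie after the last dose. They were never credited at 750 mg, yet the formula deducts them.

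The summary at stake is the one used to judge how much of the intended dose patients took. The patients concerned stopped after an unresolved interruption, so a wrong value would understate the dose they took before stopping. A moderately low value looks plausible in a table and could go unnoticed.

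**Working it through.** **Inputs.** Exposure E, the interruption term, the 750 mg/day planned intensity and the relative dose intensity (RDI) formula are from SAP Appendix 3. The 14-day gap is taken from the 2-week mark in Protocol 7.2.5. Protocol 7.2.2 sets the same 2 weeks as the limit on total interruption per cycle, and SAP Appendix 1 foresees longer ones as critical deviations. The documents report no dose-intensity result to reproduce.

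**Formula as written.** With M modified days at dose d and I interruption days at dose q:

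cumulative dose = (E − M) × 750 + M × d − I × q

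RDI = 100 × (cumulative dose / E) / 750

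At a constant 750 mg this reduces to RDI = 100 × (E − I) / E.

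**Checks where the formula works.**

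- 28 days, no event: 28 × 750 = 21,000 mg, RDI 100%.
- 28-day span with a 7-day interruption that is resumed, end date being the resumption date: (28 − 7) × 750 = 15,750 mg, RDI 75%. This is correct.

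**Interruption never resumed.** The result depends on how the interruption is recorded, which the documents do not state.

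(a) *Closed at the stop decision, after the last dose.* The patient takes 750 mg every day up to the last dose, so the true RDI is 100% in every row.

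| Dosing days E | Trailing gap I | Formula, mg | True, mg | Formula RDI |
|---|---|---|---|---|
| 112 | 14 | 73,500 | 84,000 | 87.5% |
| 56 | 14 | 31,500 | 42,000 | 75% |
| 56 | 7 | 36,750 | 42,000 | 87.5% |
| 28 | 14 | 10,500 | 21,000 | 50% |
| 28 | 7 | 15,750 | 21,000 | 75% |
| 14 | 14 | 0 | 10,500 | 0% |
| 10 | 14 | −3,000 | 7,500 | −40% |

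The shortfall is 100 × I / E percentage points, so a negative value needs I greater than E.

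With a reduction: 28 days at 750 mg, 28 days at 500 mg, then a 14-day trailing gap at 500 mg. The formula gives 28 × 750 + 28 × 500 − 14 × 500 = 28,000 mg, RDI 66.7%. The true figures are 35,000 mg and 83.3%. If the modification record also runs 14 days past the last dose (M = 42), the formula gives 14 × 750 + 42 × 500 − 14 × 500 = 24,500 mg, RDI 58.3%. Modification days therefore need the same limit.

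(b) *End date left blank.* The interruption term cannot be evaluated. The date rules in SAP 7.1.3 do not name interruption end dates. If the rule for safety events were applied, a wholly missing date would stay missing, and the patient would have no value.

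(c) *Coded only as discontinuation, or cut at the last dose.* I is about 0, RDI is about 100%, and there is no error.

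**The case against.** The strongest reply is that the formula is underspecified rather than wrong. The row is meant to give the dose actually taken, a negative dose contradicts that purpose, and a sensible programmer would read the interruption term as covering gaps inside the exposure window. Protocol 11.2 lists continuing after an interruption and discontinuing as separate actions, and SAP 7.4.1 separates adverse events leading to each, so a terminal stop may never enter as an interruption. The Drug Interruption Form is named in the Schedule of Activities, but its layout is not shown. All of this stands, and it makes the error conditional. It does not settle the matter: an investigator who interrupts while waiting for recovery does not yet know that the stop is permanent, and the SAP nowhere prescribes convention (c).

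Stronger readings are tempting, and the documents do not support them:

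- *Negative values are typical.* They need a gap longer than the whole exposure. On the QTcF route, routine ECGs in the first three cycles fall at cycle end (Protocol 9.2), about day 28, where a 14-day gap gives 50%.
- *The phase II withdrawals show how often this happens.* Protocol 4.5.2 reports 3 patients at 750 mg and 9 at 850 mg who withdrew for adverse events within one cycle. It does not say that any of them followed an unresolved interruption.
- *Every dose-modification pause is affected.* The closing rules of Protocol section 7 say "treatment should be first discontinued before undergoing a dose modification for each dose cycle", but a patient who then continues at a lower dose has the gap inside the exposure window, where the formula works.
- *Toxicity stops in general are affected, so the bias falls on apatinib.* Several toxicity stops are direct, with no interruption stage stated: LVEF below 50%, combined ALT and bilirubin elevation, hypertensive crisis and nephrotic syndrome. An excess on apatinib is plausible, but no figure in the documents measures it.

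**Conclusion.** The point holds conditionally. Appendix 3 followed literally can deduct days that lie outside the period it measures, and it gives no end date for an interruption that is never resumed. If such a gap is recorded as an interruption closed at the stop decision, RDI is too low by 100 × I / E points at a constant 750 mg: 50 points at 28 dosing days, 25 at 56 and 12.5 at 112 for a 14-day gap. If the end date is blank, the value is missing. If the stop is coded only as discontinuation or cut at the last dose, nothing is wrong.

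The number of patients concerned and their split between arms cannot be derived from the documents. The consequence is confined to the descriptive exposure summaries in SAP 7.4.2 and the dose-intensity reporting required by Protocol 7.2. Overall survival, the other efficacy endpoints and adverse-event incidences do not use these variables. The formula is explicit, can yield impossible values and is easily repaired, so it should be corrected.

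**What to change.** In SAP Appendix 3, state that only interruption and modification days between the first and last administration count. Cap each end date at the date of last administration, treat a blank end date on a never-resumed interruption in the same way, and drop interruptions that start after the last administration. A purely terminal interruption then contributes 0 days: 7,500 mg at E = 10, 21,000 mg at E = 28, RDI 100% in both.

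Alternatively, replace the formula by the sum of daily doses actually recorded from first to last administration. This is not identical to the capped formula, because it also removes the day lost in an end-minus-start count. For 500 mg on days 29 to 56 with the last dose on day 56, the capped formula counts 27 reduced days and gives 29 × 750 + 27 × 500 = 35,250 mg. The daily sum is 28 × 750 + 28 × 500 = 35,000 mg. The SAP should name which of the two is used.

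The cost is one clause and a line of code. Protocol 6.5 already has the investigator record dates and doses of administration, so no new data are needed.
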